Title:

NCT number:

2024/1/08

Study Protocol

Title: Drainage Fluid Biomarkers and Postoperative Gastrointestinal Dysfunction in Laparoscopic Colorectal Surgery. A Monocentric Prospective Observational Study

NCT number: NA yet

Study data: 2024.01.08

1. Study background

Postoperative gastrointestinal dysfunction (POGD), often referred to as postoperative ileus (POI), is a common gastrointestinal issue that frequently occurs after colorectal surgery. It is characterized by symptoms such as nausea and vomiting, abdominal distension, and delayed defecation and evacuation. The incidence of POI is not clearly defined due to the varying definitions across healthcare institutions, but it is estimated to be approximately 10-30% and is one of the most common complications after colorectal surgery (1,2). The occurrence of POI increases the nutritional risk of patients (e.g., malnutrition, myasthenia gravis, malignant morbidity), prolongs the length of hospital stay, increases hospital costs, and significantly adds to the health economic burden (3,4).

In 2018, the American Society for Enhanced Recovery and Perioperative Quality Initiative Joint Consensus Statement considered abandoning the traditional definition of POI and proposed a scoring system based on intake, sensation of nausea, vomiting, physical examination, and duration of symptoms (I-FEED). They also introduced a definition of postoperative gastrointestinal dysfunction (POGD) based on scores classifying postoperative gastrointestinal function as normal (0-2), postoperative gastrointestinal intolerance (POGI) (3-5), and postoperative gastrointestinal dysfunction (POGD) (>6) (5).

The complex pathogenesis of POGD involves a brief neurogenic phase (within 3 hours) and a more prolonged inflammatory phase (beginning at 3-4 hours and lasting for days). The inflammatory phase is crucial and is recognized as initiated by mast cells and damage-associated molecular patterns that activate macrophages in the intestinal muscle layer. Subsequently, it triggers a series of cascading inflammation reactions through the release of inflammatory factors and recruitment of inflammatory cells, which contributes to the development and exacerbation of POGD.(6-13)

Levels of inflammatory cells and factors in the peritoneal fluid are changed following abdominal surgery in both rodents and humans (14,15). Many previous studies have confirmed that the use of drainage fluids also reduces the incidence of elevated inflammatory

markers, such as CRP, in the presence of unrelated inflammatory stimuli, such as concurrent infections and systemic diseases (16,17). For instance, in other diseases like meningitis, blood IL-6 is less specific than IL-6 in the drainage fluid (18). In addition, abdominal drainage fluid is more effective and efficient than routinely collected blood for detecting anastomotic leakage (AL) following colorectal cancer surgery. However, fewer studies have been conducted to predict the recovery of postoperative gastrointestinal function by analyzing drainage fluid. We believe that analyzing postoperative gastrointestinal drainage fluid is of greater clinical importance in predicting postoperative gastrointestinal function.

In our study, we collected abdominal drainage fluid near the anastomosis on the first and third day after laparoscopic colorectal cancer surgery for biochemical and cytological tests. These tests included lactate dehydrogenase (LDH), adenosine deaminase (ADA) and albumin. We also performed conventional cytological tests for neutrophils, lymphocytes, monocytes, etc. In addition, we calculated inflammatory indices such as neutrophil-lymphocyte ratio (NLR), lymphocyte-monocyte ratio (LMR) and prognostic nutrition index (PNI). We also collected peripheral blood for the same cytological indices and evaluated the outcome of the patients' gastrointestinal function recovery using the I-FEED score. In addition, we analyzed the correlation between the above indices and PODG, and combined the inflammation indices of peritoneal drainage and serum to predict the outcome of gastrointestinal function recovery after laparoscopic colorectal cancer surgery, aiming to improve the accuracy and effectiveness of prediction and accelerate patient recovery.

2. Purpose of the study

Primary purpose: The study aims to examine the role of markers lactate dehydrogenase (LDH), neutrophil-lymphocyte ratio (NLR) as markers of inflammation, in the prediction of postoperative gastrointestinal dysfunction (POGD) in drainage fluids on day 1 following laparoscopic colorectal cancer surgery.

Secondary objective: 1. The study aims to examine the role of markers lactate dehydrogenase (LDH), neutrophil-lymphocyte ratio (NLR) as markers of inflammation, in the

prediction of POGD in drainage fluids on day 3 following laparoscopic colorectal cancer surgery.

2. The study aims to explore the correlation between albumin, adenosine deaminase (ADA), lymphocyte-monocyte ratio (LMR), prognostic nutritional index (PNI) and other inflammation indicators in drainage fluids on day 1 and day 3 following colorectal cancer surgery, and the occurrence of POGD.

3. The study aims to explore the correlation between neutrophil-lymphocyte ratio (NLR), lymphocyte-monocyte ratio (LMR), platelet-lymphocyte ratio (PLR), systemic immune-inflammatory index (SII), and other inflammation indicators in peripheral blood on day 1 and day 3 following colorectal cancer surgery, and the occurrence of POGD.

4. Combined inflammatory markers in peritoneal fluid and peripheral blood to predict POGD.

5. To evaluate the practical application of the I-FEED score in clinical practice.

3. Study endpoints

Primary endpoint:

Grading of postoperative gastrointestinal function (according to the scoring system based on intake, sensation of nausea, vomiting, physical examination, and duration of symptoms (I-FEED). normal (0-2), postoperative gastrointestinal intolerance (POGI) (3-5), and postoperative gastrointestinal dysfunction (POGD) (>6).

Secondary endpoints:

- a. Time to first postoperative deflation.
- b. Time to first postoperative bowel movement.
- c. Time to first postoperative food tolerance.
- d. Morbidity and mortality from 30-day postoperative complications .

4. Outcome Measures

Primary Outcome Measure:

Measurement of drainage fluid lactate dehydrogenase (LDH) and neutrophil to lymphocyte ratio (NLR) on postoperative day 1

Secondary Outcome Measure :

- a. Measurement of drainage fluid LDH and neutrophil to lymphocyte ratio (NLR) on postoperative day 3.
- b. Measurement of drainage fluid albumin, adenosine deaminase (ADA), lymphocyte-monocyte ratio (LMR), prognostic nutritional index (PNI) on postoperative day 1.
- c. Measurement of drainage fluid albumin, adenosine deaminase (ADA), lymphocyte-monocyte ratio (LMR), prognostic nutritional index (PNI) on postoperative day 3
- d. Measurement of blood serum neutrophil-lymphocyte ratio (NLR), lymphocyte-monocyte ratio (LMR), platelet-lymphocyte ratio (PLR), systemic immune-inflammatory index (SII) on postoperative day 1.
- e. Measurement of blood serum neutrophil-lymphocyte ratio (NLR), lymphocyte-monocyte ratio (LMR), platelet-lymphocyte ratio (PLR), systemic immune-inflammatory index (SII) on postoperative day 3.

4.Sample collection

Patient drainage fluid was collected on the first and third postoperative days. All samples were transferred to the laboratory for analysis within 30 minutes, and collected samples were aliquoted into 2 ml cryotubes and stored at -80 degrees Celsius until further use. Cytological analyses for neutrophils, lymphocytes, monocytes, etc. were performed using a Sysmex XN 1500 (Sysmex, Shanghai). Biochemical assays were performed using an AU480 chemistry analyzer (Beckman Coulter, USA) with enzyme kinetic assay for lactate dehydrogenase, peroxidase assay for adenosine deaminase and bromocresol green assay for albumin.

5.Follow-up plan

Content	Cytology (drainage fluid)	Biochemical (drainage fluid)	Biochemistry (peripheral blood)	Cytology (peripheral blood)	Consultation	medical examination	pathological results
preoperative			√	√			√
POD.1	√	√		√	√	√	
POD.2					√	√	
POD.3	√	√		√	√	√	
POD.4					√	√	
POD.5					√	√	
postoperative							√

POD: Post-operative day

6. Study Design

Study Type: Prospective single-central observational study

Observational Study Model: Case-Only

Study Start: February 18, 2024

Estimated completion date: October 1, 2024

7. Study population

7.1 Inclusion Criteria:

- Preoperative diagnosis of colorectal cancer through colonoscopy biopsy.
- Patients aged 18-80 years.
- Underwent laparoscopic radical resection for colorectal cancer with confirmed postoperative pathology.
- No prior radiotherapy, chemotherapy, or immunotherapy before surgery.
- Voluntary participation in the study and signing of a written informed consent form.

7.2 Exclusion Criteria:

- Pregnant or lactating women.
- Severe liver dysfunction (Child-Pugh class B or above); severe renal dysfunction

(serum creatinine level greater than 177).

- Patients with severe heart failure, chronic obstructive pulmonary disease, and other underlying diseases.
- Patients with pre-existing severe infections (developing sepsis or not improving after antibiotic treatment) before surgery.
- Patients with postoperative fistulas or those requiring a two-stage anastomosis.
- Intraoperative and postoperative intraperitoneal chemotherapy.
- Blood disorders (leukemia, lymphoma, aplastic anemia, etc.).
- Patient or family member withdraws midway;
- Intraoperative or postoperative instability of vital signs requires admission to the intensive care unit.
- Those with serious post-operative infections (e.g., incisional, lung, and urinary tract infections)
- Intraoperative conversion to open laparotomy.

8. Peri-operative procedures

The surgery was performed by an experienced surgeon (deputy head physician or above). The patient fasted for 6 hours and prohibited drinking water for 2 hours before the operation. General anesthesia was administered using static aspiration combined with endotracheal intubation under predominantly long-acting intravenous opioids (e.g. sufentanil). Anastomosis was performed using routine linear or circular techniques for resection of the left half of the colon, right half of the colon, sigmoid colon, and rectum, without the routine use of manual suture reinforcement. Drains were routinely placed in the post-operative period and removed after approximately 3 days post-operatively, once anastomotic fistulae and peritoneal effusion were excluded. Post-operative analgesia was provided. The patient utilized a patient-controlled intravenous paroxysmal pain regimen consisting of sufentanil (0.2ug/kg), tolstanesetron (5mg), and dizocin (20mg). Within 48 hours after surgery, the patient is allowed to consume fluids and enteral nutrition is gradually resumed as tolerated by the

patient. Patients were encouraged to mobilize early and were assisted in getting out of bed as they desired.

9. Ethics Statement

The study was conducted in accordance with the Declaration of Helsinki (as revised in 2013). The study was approved by the Ethics Committee of Chaoyang Central Hospital of China Medical University (2024 No. 02). Each subject was informed and signed an informed consent form prior to enrolment.

10. Reference

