## **5. Statistical analysis**

Statistical analyses were performed by SPSS statistical software v.17.0 (SPSS Inc., Chicago, IL, USA) and R Language v.4.0.3 (R Foundation for Statistical Computing, Vienna, Austria). Measures that met normality were expressed as mean  $\pm$  standard deviation were analyzed using the t-test, and measures that did not meet normality were expressed as median and interquartile range and analyzed using the Mann-Whitney rank sum test. The cutoff value was selected by the use of the Youden index (sensitivity + specificity - 1), and the count data were expressed as number of cases and percentages and analyzed using chi-square test. Predictors of postoperative complications and POGD were studied by univariate and multivariate logistic regression (LR). The diagnostic performance of biomarkers was assessed by receiver operator curve (ROC) analysis.

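### Day-3 drain LDH and NLR are said to predict POGD, but nothing separates patients whose POGD began before the day-3 sample

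*Protocol*

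**What the plan says.** Protocol section 2 claims prediction for LDH and NLR on both sampling days. The primary purpose is "prediction of postoperative gastrointestinal dysfunction (POGD) in drainage fluids on day 1 following laparoscopic colorectal cancer surgery", and secondary objective 1 is "prediction of POGD in drainage fluids on day 3 following laparoscopic colorectal cancer surgery". Secondary objectives 2 and 3 claim only correlation for the other markers, so the protocol uses both terms and chose the stronger one here.

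The outcome in Protocol section 3 is "Grading of postoperative gastrointestinal function (according to the scoring system based on intake, sensation of nausea, vomiting, physical examination, and duration of symptoms (I-FEED", graded as normal, intolerance or POGD. No scoring day is given. Nor do the documents say whether the worst score or a fixed-day score counts, or how the onset of POGD is dated.

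On timing, the sample collection section states "Patient drainage fluid was collected on the first and third postoperative days". The follow-up table (Protocol section 5) marks consultation and medical examination on each of POD1 to POD5.

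The exclusion criteria (Protocol section 7.2) include several postoperative events, but not POGD already present at sampling. SAP section 5 states "Predictors of postoperative complications and POGD were studied by univariate and multivariate logistic regression (LR" and "The diagnostic performance of biomarkers was assessed by receiver operator curve (ROC) analysis". It ties neither analysis to a sampling day or to onset after the sample.

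**The concern.** A marker predicts an event only if it is measured before the event. Two scheduled clinical assessments come before the day-3 sample and a third falls on the same day. A patient who reaches POGD on POD2 can therefore enter the day-3 analysis as a case, with a marker value taken after onset. If established POGD, or whatever accompanies it, goes with a higher LDH or NLR, that patient adds to the AUC although nothing was foreseen.

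What is at stake is the central claim of secondary objective 1. A day-3 AUC that looks useful could arise from a marker that only recognises patients who are already ill, and the planned analysis could not tell the two apart.

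**Working it through.** **Step 1: order of events, from the protocol's follow-up table**

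| Day | Drain sample | Consultation and examination | Position relative to the POD3 sample |
|---|---|---|---|
| POD1 | yes | yes | before |
| POD2 | no | yes | before |
| POD3 | yes | yes | same day, order not stated |
| POD4, POD5 | no | yes | after |

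POGD could be evident at two assessments before the POD3 sample. For the POD1 sample, only the same-day assessment can overlap.

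**Step 2: does any rule remove the overlap?** Protocol sections 3 and 7.2 and SAP section 5 contain no onset date, no restriction to new cases and no exclusion of patients already affected. Fixing a scoring window alone would not remove it. Under a worst score over POD1 to POD5, or a single grade on POD5, a patient affected since POD2 can still be a case.

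**Step 3: illustration of size.** The documents report no figure for this point, so every input to this step is an assumption. Let *f* be the share of POGD cases that began before the POD3 sample. Because the AUC is the probability that a random case exceeds a random non-case,

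pooled AUC = *f* × AUC(already affected) + (1 − *f*) × AUC(later onset).

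Assume no predictive value for later onset (AUC 0.50) and a 1 SD rise once POGD is present, with normal values and equal SD. Then AUC(already affected) = Φ(1/√2) = 0.760.

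- *f* = 0.25: 0.25 × 0.760 + 0.75 × 0.50 = 0.57
- *f* = 0.50: 0.50 × 0.760 + 0.50 × 0.50 = 0.63
- *f* = 0.75: 0.75 × 0.760 + 0.25 × 0.50 = 0.70

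If the marker instead separates affected patients with an AUC of 0.80 to 0.90, the pooled values are 0.575 to 0.60, 0.65 to 0.70 and 0.725 to 0.80. If *f* is 0, or the two component AUCs are equal, there is no distortion.

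For scale, the day-1 LDH planning values in SAP section 4 (1406.5 ± 70 and 1210 ± 343) imply, under normality, an AUC of Φ(196.5/√(70² + 343²)) = Φ(0.561) = 0.71. The artefact can thus be about as large as the separation the plan expects on day 1.

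**Step 4: what an analysis of later onset leaves.** SAP section 4 has 59 patients before dropout (59/0.95 = 62.1, rounded up to 63, which reproduces the plan's recruitment figure). At a ratio of 3:5, POGD cases number 59 × 3/8 = 22.1, about 22, with 37 non-cases. Cases remaining are 22 × (1 − *f*). The 95% half-width for an AUC *A* of 0.70 is 1.96 × SE, with the Hanley-McNeil SE for *m* cases and *n* = 37 non-cases:

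SE² = [*A*(1 − *A*) + (*m* − 1)(*A*/(2 − *A*) − *A*²) + (*n* − 1)(2*A*²/(1 + *A*) − *A*²)] / (*mn*).

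| *f* | Cases left | 95% half-width |
|---|---|---|
| 0 | 22 | ±0.14 |
| 0.25 | 16.5, about 16 | ±0.16 |
| 0.50 | 11 | ±0.19 |
| 0.75 | 5.5, so 5 to 6 | ±0.25 (at 6) |

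**The case against.** The strongest reply is that the outcome may be a later status. Protocol section 1 speaks of I-FEED as evaluating the outcome of gastrointestinal recovery. If the grade were taken on POD5, a POD3 sample would precede it in every patient, and predicting later status in someone already unwell is a legitimate aim. That is a possible reading, but the documents do not state it, and the secondary objectives also refer to the occurrence of POGD. Even then, a case affected since POD2 would be one of persistence, which is a different claim from foreseeing POGD.

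It is also fair to say that no onset data are given, and that neither document states that established POGD raises LDH or NLR. That limits what can be said about size. It does not supply the missing rule.

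A reader might infer four stronger points that the documents do not support:

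- **I-FEED is scored daily from POD1.** The table shows consultations and examinations only. No section links I-FEED to a day, so it cannot be said that daily scores are already collected.
- **Early onset is to be expected.** The background describes "a more prolonged inflammatory phase (beginning at 3-4 hours and lasting for days". That dates a cause, not the day on which the clinical score reaches POGD.
- **The day-1 primary purpose is equally affected.** Only same-day overlap is possible there.
- **A day-1 versus day-3 comparison would be biased.** Neither document plans one.

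**Conclusion.** The point holds for secondary objective 1. As written, the day-3 ROC and logistic regression can mix concurrent detection with prediction, because no rule separates patients whose POGD began before the sample. This follows from the visit schedule and the absence of any onset or new-case rule, and does not depend on the illustrative figures.

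The size is unknown. The pooled AUCs of about 0.57, 0.63 and 0.70 rest on three assumptions: the onset shares, an AUC of 0.50 before onset and a 1 SD rise afterwards. They show that the artefact could matter, not that it will occur. For the day-1 primary purpose the concern is confined to patients who already meet POGD on POD1, and a count with a sensitivity analysis is enough.

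**What to change.** 1. In the protocol, state the I-FEED scoring days. Record the score and the first day POGD is met at the existing POD1 to POD5 visits, and state whether each sample is drawn before that day's score.
2. In the SAP, for day-3 LDH and NLR, report the ROC for POGD first reached after the POD3 sample among patients free of POGD at sampling. Give the number already affected.
3. Describe the all-patient day-3 result as association or concurrent diagnosis, not prediction. Apply the same wording to the combined model in secondary objective 4 if it uses day-3 values.
4. For the day-1 primary analysis, report the number already in POGD at the POD1 score and a sensitivity analysis without them.

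No visit or sample is added, but this is more than a change of SAP wording, because the scoring days and onset record must enter the protocol and the report forms. The main cost is events. Under the assumed shares of 25%, 50% and 75%, about 16, 11 or 5 to 6 of 22 remain, so the day-3 predictive result is descriptive with a wide interval. At the SAP's own 5 events per variable, a model with LDH, NLR, age and TNM stage (four terms, itself an assumption) would need 4 × 5 = 20 events, more than remain at any of these shares. If the scores cannot be recorded by day, the cheaper course is to reword secondary objective 1 as association.

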## 4. Sample size calculation

In a previously published study conducted at our institution, the incidence of postoperative prolonged ileal obstruction (PPOI) was approximately 38.0% (1), a figure we approximated to be equivalent to the incidence of postoperative gastric dysfunction (POGD). The ratio of the POGD group to the non-POGD group was approximately 3:5. Sample sizes were determined based on the primary study endpoints, and the mean lactate dehydrogenase (LDH) in the POGD group on postoperative day 1 (POD.1) was  $(1406.5 \pm 70)$ , as per the pretest results. The mean LDH for the non-POGD group was  $1210 \pm 343$ . Utilizing a one-sided, two-sample unequal-variance t-test with a power of 0.8 and an  $\alpha$ -value of 0.05, calculated using PASS2021 (NCSS, USA), the required number of cases was determined to be 45. The Neutrophil-to-Lymphocyte Ratio (NLR) value for the POD.1 POGD group was  $(156.3 \pm 14.7)$ , while the mean NLR value for the non-POGD group was  $(39.4 \pm 37.5)$ . The calculated sample size for this comparison was 8 cases, with a maximum sample size of 45 cases. In this study, age and TNM stage were primarily controlled as confounders. Assuming that 5 event samples are required to control for each variable, an additional sample of 14 cases is necessary,

bringing the total required sample size to 59 cases. Considering a 5% dropout rate, the final recruitment requirement is 63 cases.

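### As supplied, the I-FEED bands of the primary endpoint (0-2, 3-5, >6) give no grade to a total of exactly 6, and the available SAP text states no score range for POGD

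*Protocol*

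**What the plan says.** Protocol section 3 makes the grading of postoperative gastrointestinal function by I-FEED the primary endpoint. It names three levels: normal at 0-2, then "postoperative gastrointestinal intolerance (POGI) (3-5), and postoperative gastrointestinal dysfunction (POGD) (>6". The background in protocol section 1 prints the same bands and attributes them to reference 5: "normal (0-2), postoperative gastrointestinal intolerance (POGI) (3-5), and postoperative gastrointestinal dysfunction (POGD) (>6) (5". Section 1 also says that the study evaluated "gastrointestinal function recovery using the I-FEED score". Secondary objective 5 in protocol section 2 is "To evaluate the practical application of the I-FEED score in clinical practice".

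The SAP works with two groups, POGD and non-POGD. Section 4 takes the POGD incidence from a 38.0% figure for prolonged ileus, "a figure we approximated to be equivalent to the incidence of postoperative gastric dysfunction (POGD", and adds that "The ratio of the POGD group to the non-POGD group was approximately 3:5". It gives pretest LDH and NLR values for each group without saying which score put a patient in which group. In section 5 the one cut-off mentioned concerns the markers: "The cutoff value was selected by the use of the Youden index". POGD is also a regression outcome: "Predictors of postoperative complications and POGD were studied by univariate and multivariate logistic regression (LR".

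**The concern.** A grading scale should place every possible total in exactly one grade. Here the POGI band stops at 5, which implies that POGD starts at 6, while the POGD band as printed starts above 6. Both cannot be complete. Two people grading the same patient with a total of 6 could each point to the protocol and code that patient differently.

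The gap lies at the boundary that matters most. POGD or not is the split in the sized LDH and NLR comparisons, the condition that the markers are meant to predict, and an outcome of the logistic regression. If the boundary is still open when the marker data are seen, the data could influence the choice. Secondary objective 5, which evaluates the score itself, also needs bands that cover every total.

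**Working it through.** **1. Apply the printed bands to each whole-number total.**

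| Total | Bands as printed | If the last band were inclusive of 6 |
|---|---|---|
| 0, 1, 2 | normal | normal |
| 3, 4, 5 | POGI | POGI |
| 6 | none | POGD |
| 7 and above | POGD | POGD |

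The only gap is at 6, and it depends entirely on the strict sign. The last column shows this dependence; it does not say which rule is right.

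**2. Look for a rule elsewhere.** Protocol sections 1 and 3 agree with each other, so neither resolves the other. The available SAP text does not mention I-FEED and gives no score range. The Youden cut-off in SAP section 5 is chosen from sensitivity and specificity and reads as a marker threshold.

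**3. Expected groups.** Inputs from SAP section 4: 59 patients before dropout and 38.0% incidence, itself a prolonged-ileus figure used as an approximation. 59 × 0.38 = 22.4, so about 22 POGD and 37 non-POGD.

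**4. Limits on diagnostic accuracy.** Suppose k of the 22 score exactly 6 and the literal rule moves them to non-POGD. At a fixed marker cut-off, and without assuming any distribution:

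- change in sensitivity ≤ k/22
- change in specificity ≤ k/(37 + k)

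For k = 1 these are 1/22 = 4.5 points and 1/38 = 2.6 points. They are upper limits, reached only in extreme configurations.

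**5. Effect on the sized LDH comparison.** Inputs from SAP section 4: POGD 1406.5 ± 70, non-POGD 1210 ± 343, one-sided unequal-variance t-test, α = 0.05. Power comes from the noncentral t distribution.

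- Base case, 22 versus 37: difference 196.5; SE = √(70²/22 + 343²/37) = 58.3; power 95.2%.
- Illustration with k = 6, where each 6 has the POGD distribution: groups of 16 and 43. The share of moved patients in the non-POGD group is w = 6/43 = 0.140. Its mean is 1210 + 0.140 × 196.5 = 1237.4. Its SD is √(0.860 × 343² + 0.140 × 70² + 0.140 × 0.860 × 196.5²) = 326.4. The difference is 169.1; SE = √(70²/16 + 326.4²/43) = 52.8; power 93.5%.
- The same calculation gives 95.0% for k = 1 and 94.5% for k = 3.

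The values of k are illustrative, since the documents give no score distribution. The calculation also assumes that the pretest grouping counted a 6 as POGD, which the SAP does not say.

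**The case against.** **The sign may be a reading artefact.** The whole gap rests on one character, and a greater-than-or-equal sign may have lost its lower stroke when the PDF was read. The same sign in two sections does not rule out a systematic loss. This stands as a caveat: the supplied text cannot settle it, so checking the source comes before any edit. If the source does print an inclusive sign, the gap closes, but the available SAP text would still state no score range for POGD.

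**The binary analyses already have a literal rule.** POGD is above 6, everything else is non-POGD, and no ordinal analysis is described. This is right as far as it goes, and a reader should not infer that a patient with a 6 must drop out of the regression or the ROC analysis. It does not remove the conflict. The primary endpoint is a three-level grading in which a 6 has no level, and the POGI band contradicts the literal rule.

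**A total of exactly 6 may not occur.** The I-FEED item scores are not in the documents, so both whole-number totals and the possibility of a 6 are inferred from the printed bands. This also stands as a caveat.

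**The pretest may have used the printed rule.** If its POGD group was formed with totals above 6, the SAP inputs already match that rule and the shift in step 5 does not arise. That is correct, and it is why the SAP should say how the pretest groups were formed.

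**Conclusion.** The point holds as an internal inconsistency in the endpoint definition: as supplied, the bands are wrong as written, because a total of exactly 6 falls in no grade and the available SAP text does not settle it.

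The number of patients affected is unknown. With about 22 expected POGD patients, each relabelled patient can move sensitivity at a fixed cut-off by at most about 4.5 points. The effect on the sized LDH comparison is likely small if a 6 resembles the POGD group: 95.2% to 93.5% with six such patients. For totals of 6 with intermediate LDH values the SAP gives no inputs, and no power figure is offered.

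Two stronger conclusions might be inferred, and the documents support neither. One is that the gap undermines the sample size; the calculation above does not show that. The other is that the SAP nowhere defines POGD by score. One part of the SAP was not available, so the statement covers only the text that was.

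**What to change.** Before analysis, and without reference to marker data:

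1. Check the original protocol file for the printed sign, and the cited definition (protocol reference 5) for the intended boundary.
2. Reconcile the POGI and POGD bands so that they are contiguous and exhaustive, and print the same rule in protocol sections 1 and 3.
3. State the resulting POGD and non-POGD score ranges in SAP sections 4 and 5, and say in section 4 which rule formed the pretest groups.
4. As a useful addition, report how many patients scored exactly 6. A sensitivity analysis with those patients under the other assignment is optional.

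The cost is one source check and short text edits in two protocol sections and two SAP sections. No extra patients or measurements are needed.

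### The 30-day morbidity and mortality endpoint has no scheduled assessment after POD5, and the exclusions remove major complications, so the rate is biased downward if the plan is followed as written

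*Protocol*

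**What the plan says.** Protocol section 3 gives endpoint d, the last of four secondary endpoints, as "Morbidity and mortality from 30-day postoperative complications".

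The table under "5.Follow-up plan" ticks consultation and medical examination on each of POD1 to POD5. One later row, labelled only as postoperative and without a date, ticks the "pathological results" column and nothing else. Neither document describes a day-30 visit, call, readmission check, record review or vital-status check. SAP sections 6 and 7 deal with recording and storing data, not with finding events.

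Protocol section 7.2 excludes three groups for what happens after surgery:
- "Patients with postoperative fistulas or those requiring a two-stage anastomosis"
- "Those with serious post-operative infections (e.g., incisional, lung, and urinary tract infections"
- "Intraoperative or postoperative instability of vital signs requires admission to the intensive care unit" (this one also covers intraoperative events)

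SAP section 5 plans a regression on complications: "Predictors of postoperative complications and POGD were studied by univariate and multivariate logistic regression (LR". It gives no time window for complications and does not mention endpoint d.

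**The concern.** An endpoint defined over 30 days needs a procedure that looks at all 30 days, in a population that can still have the event. The schedule does not provide the first, and the exclusion list undermines the second.

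At stake is what the report can claim. A figure published as 30-day morbidity and mortality would mainly describe the first five days in patients selected for not having had a fistula, a serious infection or an intensive care admission. A reader comparing it with other 30-day rates would be misled in a known direction. If the SAP's complication model takes this endpoint as its outcome, patients with late events would also enter it as non-events.

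**Working it through.** **1. The plan's own figures.** The documents state no complication rate, event count or 30-day follow-up figure. The only related number is the sample size in SAP section 4, which reproduces: 45 + 14 = 59 evaluable patients, and 59 / (1 − 0.05) = 62.1, rounded up to 63.

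**2. Coverage of the window.** Days 1 to 5 have a scheduled clinical assessment and days 6 to 30 have none: 30 − 5 = 25 days, and 25/30 = 83% of the calendar window. This is a share of days, not of risk.

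**3. Direction of bias from the schedule.** Endpoint d is cumulative. A patient whose only complication arises after POD5 and is not found is counted as event-free, so this error can only lower the rate.

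**4. Direction of bias from the exclusions.** Let N patients have surgery, E of them have a complication, and X of those E be excluded because of it. The rate changes from E/N to (E − X)/(N − X). The second is smaller when N(E − X) < E(N − X), which reduces to E < N. So it is lower whenever X > 0 and not every patient has a complication. This assumes that the excluded conditions would count as complications; the protocol gives no definition, but fistula and serious infection are hard to read otherwise.

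**5. Both together.** With L further patients whose late events are missed, the recorded rate is (E − X − L)/(N − X). X and L are separate terms, so adding follow-up reduces L and leaves X as it is.

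**6. Illustration of the schedule effect only.** The documents give no inputs, so both the true 30-day rate (10 to 30%) and the share of events seen by POD5 (25 to 75%) are assumptions, as is no capture at all after POD5. With 59 patients, recorded events = 59 × rate × share:

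| Assumed true rate | Full capture | 75% by POD5 | 50% by POD5 | 25% by POD5 |
|---|---|---|---|---|
| 10% | 5.9 | 4.4 (7.5%) | 3.0 (5.0%) | 1.5 (2.5%) |
| 20% | 11.8 | 8.9 (15.0%) | 5.9 (10.0%) | 3.0 (5.0%) |
| 30% | 17.7 | 13.3 (22.5%) | 8.9 (15.0%) | 4.4 (7.5%) |

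Under POD5-only capture the recorded count runs from 1.5 to 13.3, too wide a range to support any single estimate.

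**7. Conditional consequence for the regression.** SAP section 4 works with five events per variable: "Assuming that 5 event samples are required to control for each variable, an additional sample of 14 cases is necessary". If that rule were applied to a model of endpoint d, full capture would support 1, 2 or 3 terms at true rates of 10, 20 or 30%. POD5-only capture would support 0, 1 or 2 terms at a 75% share, 0, 1 or 1 at 50%, and none at 25%. The SAP does not state that endpoint d is the outcome of that model.

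**The case against.** The strongest reply is that the follow-up table was never meant as a complication schedule. It has no column for complications or vital status on any day, and none for first flatus, bowel movement or food tolerance, which are endpoints a to c. On that reading the plan has only left the ascertainment method unstated. Discharge day is not given either, so some days after POD5 may be inpatient days on which events would be noticed.

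Part of this stands. Not all of the 25 days need be unobserved, and the finding concerns the plan as written, not what the site might do in practice. But no other process is written down, and informal detection would probably be uneven: Protocol section 1 says that ileus lengthens the hospital stay, so patients with POGD could be watched for longer than those without. The reply also does not touch the exclusions, which are explicit.

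A second objection is that schedule and exclusions are different defects. They are, and working step 5 keeps them apart. They belong in one point because both act on the same reported rate, and repairing one leaves the other in place.

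A third is that endpoint d is minor. It is secondary, it does not appear among the objectives or the listed outcome measures, and it plays no part in the sample size. That stands and limits the weight of the point.

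**Conclusion.** The point holds as a conflict between a stated endpoint and a stated schedule and exclusion list. Followed as written, the plan gives a 30-day rate that is biased downward, for two separate reasons. The direction rests on two assumptions: that some complications arise after POD5 and go unfound, and that the excluded conditions would otherwise count as complications.

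Three stronger readings are tempting and are not supported:
- **A specific size of understatement.** A reader might take one cell of the table, such as 20% recorded as 10%, as an estimate. It depends on an assumed rate, assumed timing and no capture after POD5. The 83% of unscheduled days does not mean that 83% of events are missed.
- **Damage to the planned complication model.** SAP section 5 does not define its complication outcome or tie it to 30 days. Late events coded as non-events are a consequence only if that model uses endpoint d.
- **A threat to the main result.** The primary LDH/NLR analysis for POGD does not use endpoint d and is unaffected by this gap in its ascertainment.

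The change should be made, but it concerns a secondary endpoint.

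**What to change.** Add a POD30 row to the follow-up table: a telephone call plus a check of records and vital status. State how a complication is defined and graded, and how patients not reached by day 30 are handled.

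For endpoint d, count complications and deaths in all enrolled patients who had surgery and have not withdrawn consent, including those excluded from the biomarker analysis for a postoperative event. The section 7.2 exclusions can still define the biomarker population. The POD30 row alone would not be enough, because it leaves the exclusion bias in place.

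In SAP section 5, say whether the complication regression uses endpoint d and over what window.

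If POD30 contact is not done, relabel the endpoint as complications through POD5 in patients without the excluded events, and drop the 30-day claim.

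The cost of the first option is a short amendment and about 63 brief contacts or chart checks at one centre. The cost of the second is a less ambitious secondary endpoint. Neither changes patient care or the primary analysis.
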